2. LAY SUMMARY

Liver transplantation is a highly effective treatment, but the supply of suitable donor organs is greatly exceeded by the number of patients who would benefit. More than 10% of patients on the waiting list die before receiving a transplant and many others are never placed on the list because access is restricted to patients with the best chance of success.

Less than 2/3 of deceased donors in the UK result in a liver transplant, because the livers from many donors are less suitable, due to older age, medical conditions or circumstances of death, and are much more likely to cause complications. To use these higher-risk livers safely, we need to find better ways to preserve, repair and test livers so that more of the available donor organs can be transplanted without compromising the survival rate.

Normothermic machine perfusion (NMP) is a novel method of organ preservation which replaces the conventional icebox, using a machine which restores the flow of blood at body temperature allowing the liver to function during storage. This results in (i) better preservation of the liver (less injury), (ii) repair of the donor organ (reconditioning), and (iii) assessment of the organ's functional state (viability assessment).

Previous studies, from the UK and elsewhere, showed a substantial reduction in injury. They also suggested that transplant surgeons could accept higher risk organs with confidence, mainly due to the ability to assess function prior to transplant. However, these studies were not primarily designed to test the effects of NMP on organ use, and there remains a crucial need for high-quality evidence as to whether this more complex and expensive technology should become the standard of care.

The UK-designed and manufactured NMP device proposed in this study has already been used in small numbers of transplants in all of the UK's seven liver transplant units. This has mostly relied upon charitable funding, because this technology has not yet been funded by NHS commissioners.

In this study, we will identify offers of those donor livers less likely to be used and make the NMP machine available for storage and assessment. We will compare the proportion resulting in successful transplants with a group of offers where NMP was not used to see if a pre-defined threshold for increased use is met. We will also collect information about the overall cost of the new technology compared to the old, so that the NHS can decide whether NMP is good value for money.

3. SYNOPSIS

Trial Title	Utilisation of normothermi livers - a national threshold-	c machine preservation in ex-	ktended criteria	
Internal ref. no. (or short title)	Perfused Liver Utilisation Study (PLUS)			
Trial registration	ISCRTN 11552402			
Sponsor	University of Oxford			
Funder	NIHR Invention for Innovation	on Challenge Awards (NIHR20)	1003)	
Clinical Phase	Phase III			
Trial Design	Threshold-crossing design w	rith a prospectively-defined eff	ficacy threshold.	
	Control cohort (static cold storage; SCS): A priori defined real-world control cohort meeting study inclusion criteria, identified from UK Transplant Registry held by NHS Blood and Transplant (referred to as 'the registry' throughout the protocol. Study cohort (normothermic machine perfusion; NMP): Prospectively identified, consecutive liver offers with a donor utilisation index (DUI) >			
	0.27 (appendix 3), in which	NMP is made available	. ,	
Trial Participants	Extended criteria (DUI > 0.27) liver offers made to participating centres through the NHSBT offering system			
Sample Size	Control cohort: 2465 (retrospective) Study cohort: 1035 liver offers (prospectively recruited in this study)			
Planned Trial Period	Total study: 01/10/2021 – 30/09/2026 (60 months) Participant follow-up: 12 months. Long-term patient and graft survival will be assessed using registry data at 5 years post-transplant			
Planned Recruitment period	11/04/2022 – 11/10/2023 (18 months)			
·	Objectives	Outcome Measures	Timepoint(s)	
Primary	To assess whether NMP can increase the availability of livers for transplantation without compromising outcome	Functional utilisation – transplantation of the liver with 12-month patient and graft survival	12 months post- transplant	
Secondary	To assess the cost-	Intervention costs	Pre-	
	effectiveness of NMP in the context of NHS	NHS Resource Use	transplant, Day 7,	
	commissioning guidelines	Quality of Life	Months 3 and 12	
	To assess biochemical liver function in the study	Biochemical liver function (ALT, GGT, INR, Bilirubin)	Days 1-7,	
	cohort	Daily serum lactate (whilst on ITU/HDU)	Month 12	
		Model for Early Allograft Function score (MEAF)		

	To compare graft and	Primary non-function	Day 7,
	patient survival between study and control cohorts.	Graft survival (death censored)	Months 3 and 12. Long-term (5 year).
		Graft survival (non- censored)	
		Patient Survival	
	To compare the use of	Length of ITU/HDU stay	Days 1-7,
	hospital resources between study and	Length of hospital stay	discharge from hospital.
	control cohorts	Need for renal replacement therapy	n om nospitan
	To assess the ability of perfusion parameters and biomarkers in perfusion fluids to predict clinical outcomes following	Perfusion parameters (pressures, flows, bile production, pH, pO ₂ , pCO ₂ blood temperature, glucose)	During preservation (refer to section 9.7.2)
	transplantation.	Perfusate ALT	
		Perfusate lactate	
		Perfusate cell-free DNA levels (cfDNA)	
		Post-reperfusion liver histology, including degree of macrosteatosis	
	To assess safety in the	Organ discard rate	Days 1-7,
	study and control cohorts	Perfusate cultures	Months 3 and 12
		Adverse outcome rates	

4. ABBREVIATIONS

AE	Adverse event
ALP	Alkaline Phosphatase
ALT	Alanine Transaminase
AST	Aspartate Transaminase
cfDNA	Cell-free DNA
CI	Chief Investigator
CRF	Case Report Form
СТ	Clinical Trials
СТА	Clinical Trials Authorisation
DBD	Donation after Brain Death
DCD	Donation after Circulatory Death
DLI	Donor Liver Index
DMC/DMSC	Data Monitoring Committee / Data Monitoring and Safety Committee
DUI	Donor Utilisation Index
EAD	Early Allograft Dysfunction
ECD	Extended Criteria Donor
EQ-5D-5L	EuroQoL 5 dimension 5 level health-related quality of life instrument
GCP	Good Clinical Practice
GGT	Gamma-Glutamyl Transpeptidase
GP	General Practitioner
GST	Glutathione S-Transferase
HD	Haemodialysis
HDF	Haemodiafiltration
НЕАР	Health economics analysis plan
HF	Haemofiltration
HRA	Health Research Authority
ICF	Informed Consent Form
ICH	International Conference on Harmonisation
IFU	Instructions For Use
INR	International Normalised Ratio
IRB	Independent Review Board

IVC	Inferior Vena Cava
MEAF	Model for Early Allograft Function
МАР	Mean Arterial Pressure
MELD	Model for End-stage Liver Disease
NHS	National Health Service
NHSBT CTU	NHS Blood and Transplant Clinical Trials Unit
NMP	Normothermic Machine Preservation
NRP	Normothermic Regional Perfusion
PGD	Primary Graft Dysfunction
PI	Principal Investigator
PIL	Participant/ Patient Information Leaflet
PNF	Primary Non-Function
QALY	Quality-adjusted life year
R&D	NHS Trust R&D Department
REC	Research Ethics Committee
RGEA	Research Governance, Ethics and Assurance
RRT	Renal Replacement Therapy
SAE	Serious Adverse Event
SAP	Statistical Analysis Plan
SCD	Standard Criteria Donor
SCS	Static Cold Storage
SDV	Source Data Verification
SNOD	Specialist Nurse for Organ Donation
SOP	Standard Operating Procedure
TMF	Trial Master File
TSC	Trial Steering Committee
UW	University of Wisconsin

5. BACKGROUND AND RATIONALE

5.1. Liver transplantation in the United Kingdom

The dominant challenge in current-day clinical organ transplantation is the shortage of deceased donor organs. Although the number of organ donors has increased by 95% over 10 years (a result of concerted public education, NHS investment and political commitment), there remains a major discrepancy between demand and supply. The liver transplant waiting list has remained largely static over the past 10 years, with 432 patients waiting at 31st March 2019 (1).

Liver disease is increasing and contributed to 13,417 deaths in England and Wales in 2017: as a result, the demand for liver transplantation is growing. Meanwhile donor livers being offered for transplant are progressively more marginal, in terms of hypoxic injury, obesity, cardiovascular disease and age: the proportion of donors with high-risk factors known to be associated with inferior outcomes and higher discard rates has increased from 8% (2007) to 39% (2018). Because of this, only 62% of deceased donors in the UK result in a liver transplant.

Around 3% of patients on the national waiting list die before a suitable donor organ becomes available. Indeed, this under-estimates the problem because access to the liver transplant waiting list is restricted to only those patients most likely to benefit. Many more patients who would nonetheless benefit from a transplant, such as some with primary or metastatic cancer, are not placed on the waiting list in order to focus scarce donor resources on patients with the best prognosis.

5.2. Utilisation of extended-criteria livers

A recent study based on UK registry data developed a Donor Liver Index (DLI) to predict graft survival from donor demographic factors (2). Recent analysis shows that livers in the upper half of DLI (> 1.61) demonstrate not only worse graft survival, but also lower utilisation than those in the lower half of DLI (19% vs 77%).

Whilst this study demonstrates a clear link between donor risk and utilisation, the DLI was not primarily intended as a score for utilisation (proportion of livers offered that are transplanted). Further analysis of NHSBT data has demonstrated factors leading to poor utilisation of DBD and DCD livers, leading to the development of a Donor Utilisation Index (DUI; Appendix 3). Many of the factors linked with poor graft survival are also associated with poor utilisation, although there are some differences and these factors differ between DBD and DCD livers. Analysis of historical data (from 01/02/2016 to 31/01/2019) demonstrates that utilisation of livers in the top 60% of DUI (represented by a DUI > 0.27) is just 26% compared with 85% for livers in the lower 40% of DUI (DUI<=0.27). These data exclude livers not eligible/suitable for NMP (donors from outside of the UK, HIV or hepatitis C positive donors, and paediatric donors).

5.3. Normothermic Machine Preservation (NMP)

Preservation of donor organs for transplantation is currently based on cooling to ice temperature with a specialist solution and storage in an ice box (static cold storage; SCS). Whilst satisfactory for organs of

Clinical Trial Protocol Template version 14.0

optimal quality, it is a major limitation in the context of the suboptimal donor organs that form an increasing proportion of current transplant practice.

An extensive experimental programme of development of the NMP technology showed this to be a superior means of liver preservation, which also allowed accurate viability prediction by means of functional testing during perfusion (3). The first patient to receive a liver transplanted after normothermic preservation underwent surgery in 2013 (4).

This Phase 1 study was followed by a randomised controlled trial, comprising 220 transplanted livers across seven European liver transplant centres, providing a direct comparison between conventional (icebox) static cold storage (SCS) and normothermic perfusion (5). This demonstrated a significant reduction in biochemical markers of transplant-associated liver injury (the primary endpoint of the trial and a surrogate marker of graft survival), as well as a 50% reduction in the proportion of organs that were discarded (12% versus 24%). Notably livers in the normothermic arm were preserved for 54% longer than those in the control arm, implying considerable logistic benefits. NMP was safe, with no excess of adverse events in either arm.

The OrganOx metra NMP device, used in the studies described above, is now commercially available and has been used outside the trial environment in all of the UK's seven liver transplant centres. In January 2019, NICE approval was granted for oxygenated machine perfusion of the liver to be used 'with special arrangements for clinical governance'. However, at present NMP of the liver is not routinely funded by NHS commissioners, and liver transplant units wishing to use this technology are essentially dependent upon charitable funding.

5.4. Liver utilisation with NMP

The phase III study described above provide strong circumstantial evidence that NMP increases the utilisation of high-risk donor organs. Experience during the trial suggested that surgeons were able to transplant a higher proportion of high-risk organs (i) by selecting viable organs by having access to functional parameters and (ii) because of improved viability of NMP organs. However this trial was not designed or intended to test the impact of NMP on organ discard: not least because all organs accepted for the trial had to be deemed transplantable following either method of preservation. High-risk livers that were not suitable for cold storage were excluded from the trial, although these are the very livers that may benefit the most from improved preservation and viability assessment.

Other, non-randomised, studies have since corroborated the evidence of improved organ utilisation. In a Phase-2 study from Birmingham (VITTAL), 22 of 31 perfused livers, previously declined by every UK liver transplant unit, were deemed transplantable based upon functional testing during perfusion, and were transplanted with immediate function (6). Evidence from Cambridge shows a 25% increase in overall liver transplant rate following introduction of NMP for high-risk donor organs (personal communication [name]).

There are several mechanisms by which NMP may be able to improve organ utilisation:

NMP allows longer preservation without detriment to organ quality. Transplantation of marginal
organs currently necessitates very short storage times: transport and other logistic factors often

- render this unfeasible. Transplantation of high-risk donor organs after preservation of 24 hours (allowing daytime surgery) has been shown to be feasible using NMP by several groups (7)
- Reconditioning of damaged organs during perfusion. NMP restores cellular energy following hypoxia, reducing ischaemia-reperfusion injury at the time of implantation. Similarly, NMP mitigates the severe ischaemia-reperfusion associated with transplantation of steatotic (fatty) livers (such organs are very often declined) (personal communication [name]).
- NMP provides the transplant surgeon with viability data. Real-time information about the metabolic function of the liver immediately before the transplant (e.g. clearance of lactate and biochemistry of the bile produced) correlates with post-transplant performance (8). This has resulted in the successful transplantation of livers that would not otherwise have been transplanted (6).
- NMP provides the surgeon with more time. In contrast to the maximum urgency with which high-risk organs are currently transplanted in order to minimise cold preservation injury, NMP allows the final decision to transplant a high-risk organ to be deferred until more information is available.

5.5. Summary

Whilst previous studies have demonstrated efficacy and safety of NMP and suggested an increase in the proportion of livers transplanted, none have been specifically designed to quantify the impact of availability of NMP on organ utilisation. Given the additional cost and logistical burden that NMP brings over the simplicity of static cold storage, it is important to quantify the clinical and health economic impact of NMP in the NHS setting. Given the very low utilisation in extended-criteria livers with a high DUI, it would make sense to target these liver offers as the potential yield of additional transplants will be highest.

This study will achieve this by recruiting livers at the point of offering and assessing the impact of availability of NMP on the entire transplant pathway. The use of functional utilisation as a novel endpoint will assess the impact of NMP on organ utilisation and transplant rate, whilst ensuring that the additional transplants do not come at the cost of inferior clinical outcomes.

6. OBJECTIVES AND OUTCOME MEASURES

6.1. Primary Objective and Outcome Measure

Objective	Outcome Measures
To assess whether NMP can increase the availability of livers for transplantation without compromising outcome	Functional utilisation – transplantation of the liver where the patient is alive, without the need for a retransplant, 12 months postoperatively.

6.2. Secondary Objectives and Outcome Measures

Objective	Outcome Measures
To assess the cost- effectiveness of NMP in the context of NHS commissioning guidelines	 NMP versus SCS intervention costs NHS resource use, measured by documentation of inpatient and outpatient episodes and treatments at study timepoints, data collected for patients on the transplant waiting list, historically published data and hospital episode statistic (HES) data; valued using standard NHS unit costs Health-related quality of life for patients on the waiting list and post-transplant, assessed by completion of the EQ-5D-5L questionnaire
To assess biochemical liver function in the study cohort	 Daily serum bilirubin, GGT, ALT and INR at days 1-7 following transplantation. Daily serum lactate at days 1-7 whilst in high level (ITU/HDU) care Serum bilirubin, ALP, ALT and AST at month 12 following transplantation. Model for Early Allograft Function (MEAF) score (9): a composite score based upon the maximum values of ALT, INR and bilirubin during the first 3 days postoperatively.
To compare graft and patient survival between study and control cohorts	 Primary non-function: graft failure during the first 10 days after liver transplantation, documented by the site team as PNF with no initial function Graft survival (death censored) at 7 days, 3 and 12 months and 5 years following transplantation (defined as a functioning transplant in the absence of death and re-transplantation). Graft survival (non-censored) at 7 days, 3 and 12 months and 5 years following transplantation (graft loss includes death or retransplantation) Patient survival at 7 days, 3 and 12 months and 5 years following transplantation.
To compare the use of postoperative hospital	 Length of stay in high level (HDU/ITU) care post-transplant Length of initial hospital stay post-transplant

resource between study and control cohorts	Need for renal replacement therapy (haemodialysis, haemofiltration, haemodiafiltration)
To assess the ability of perfusion parameters, biomarkers in perfusion fluids and graft histology to predict clinical outcomes following transplantation.	 Perfusion parameters (logged automatically by the device): a. Arterial and caval pressures (in mmHg) b. Arterial, portal and caval flow rates (in L/min) c. pO₂, pCO₂ and pH d. Blood temperature (°C), Glucose (mmol/L) and bile production (ml/h) Perfusate ALT at time zero, 2 and 4 hours, and the end of NMP Perfusate lactate at time zero, 15 min, 1, 2 and 4 hours, and end of NMP Note: time zero is when the liver is put onto the OrganOx metra Perfusate cell-free DNA (cfDNA) levels during perfusion at 2 and 4 hours Graft histology, including degree of macrosteatosis, following reperfusion
To assess safety in the study and control cohorts	 Organ discard rate Perfusate culture. At the end of preservation a sample will be taken for microbiological culture (NMP livers only). Adverse outcome rates. Severity will be graded according to the Clavien-Dindo classification for any reported as SAEs for the study cohort (10) Recipient infection Biopsy proven rejection Biliary complications (biliary strictures or bile duct leaks) requiring intervention Vascular complications requiring intervention (bleeding, hepatic artery stenosis, hepatic artery thrombosis, portal vein thrombosis, portal vein stenosis) Reoperation rate

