- Serum alkaline phosphatase (ALP; measured in IU/L)
- Blood urea (mmol/L)
- Serum creatinine (μmol/l)

Safety outcomes

Safety outcomes that are not part of routine registry collection and will be collected for the study:

- Biopsy-proven rejection episodes and treatment
- Biliary complications
 - Biliary strictures anastomotic and non-anastomotic. Both radiologically diagnosed and clinically apparent strictures
 - Bile duct leaks. Defined as those requiring drainage, refashioning of anastomosis or stenting.
- Vascular complications
 - o Haemorrhage. Defined as bleeding requiring reoperation
 - Hepatic artery thrombosis. Defined as formation of new clot resulting in graft dysfunction or loss, or requiring pharmacological, radiological or surgical intervention.
 - o Portal vein thrombosis. Defined as formation of new clot resulting in graft dysfunction or loss, or requiring pharmacological, radiological or surgical intervention.
 - IVC/Hepatic vein occlusion. Defined as venous occlusion resulting in graft dysfunction or loss, or requiring radiological or surgical intervention.
- Reoperation rate

Immunosuppression

Details of maintenance immunosuppression at 12 months post-transplant will be based on data routinely collected by the registry.

9.8.4. 5-year outcomes

Whilst the end-point for trial participation will be 12 months, patients will also be consented for ongoing follow-up by linkage to outcomes recorded by NHS Digital and in the UK Transplant Registry. Registry data will be used to collect:

- Patient survival at 5 years post-transplant.
- Graft survival (death censored) at 5 years post-transplant (defined as a functioning transplant in the absence of death and re-transplantation).
- Graft survival (non-censored) at 5 years post-transplant (graft loss includes death or retransplantation)

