12.2. Anticipated Serious Adverse Events

Liver transplantation is a life-saving procedure but is associated with serious life-threatening complications which would be expected during the study and which we do not propose to report as SAEs, except those reported as outcomes:

- Primary non function: 0.8% in DBD, 4.0% in DCD livers
- Early allograft dysfunction (Olthoff definition): 25% DBD, 40% DCD
- Hepatic artery thrombosis: 4-15%, depending whether anomalous arterial supply required reconstruction or not
- Post reperfusion syndrome: 30%, more common in DCD than DBD
- Biliary anastomotic breakdown in 10%, more common in DCD
- Post operative haemorrhage requiring reoperation: 10%
- Acute rejection: 20%
- Acute kidney injury: 25% in DBD, 50% in DCD
- Chest complications: sepsis; effusion; paralysed right hemidiaphragm: common
- Ascites: universal if pre-existing ascites, common if not pre-existing
- Line sepsis
- Biliary anastomotic stricture: 10%
- Ischaemic cholangiopathy: 4% DBD, 20-25% DCD
- Retransplantation in first year: around 11% for DBD, rising to 17% for DCD
- Graft failure or sepsis
- Hospitalisation for pre-existing condition that has not deteriorated.

The investigator will exercise their medical judgment in deciding whether an abnormal laboratory finding or other abnormal assessment is clinically significant. However, if in the opinion of the investigator, the frequency or severity of the event is greater than would be expected then it must be reported.

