Secondary outcomes will be presented using descriptive statistics and analysed using a similar approach, with adjustment for donor type and use of NRP. However, when performing analyses on the subset of transplanted livers, adjustment will also be made for the transplanting centre where numbers allow. General Linear and Generalised Linear Models or non-parametric methods will be used as appropriate for the different outcomes. Length of HDU/ITU and hospital stay post-transplant will be analysed using a competing risks approach where death is the competing risk. Measures of biochemical liver function at 12 months will be compared between the two treatment arms using linear regression, with appropriate transformation if required. Patient and graft survival (censored and non-censored) will be estimated using the Kaplan-Meier method and analysed using Cox Proportional Hazards regression. Safety outcomes will be summarised for each arm according to classification and severity. Some outcomes are only measured in the study arm and these will be presented using descriptive statistics. Measures of biochemical liver function over the first seven days will be presented graphically and area under the curve summarised for the study arm, along with a summary of the MEAF score.

During the trial, data will be collected regarding perfusion parameters (including machine logs and perfusate characteristics). These data will be analysed separately to the main clinical trial outcomes to explore relationships between perfusion parameters, utilisation and transplant outcomes.

Clinical Trial Protocol Template version 14.0

CONFIDENTIAL

© Copyright: The University of Oxford and Oxford University Hospitals NHS Foundation Trust 2018

After the final patient has reached five years post-transplant, patient and graft survival will be obtained from the transplant registry. The unadjusted survival rates at five years will be estimated using the Kaplan-Meier method. A Cox proportional hazards model will also be used to assess the treatment effect after risk-adjustment for any imbalance in baseline characteristics that is known to affect recipient outcome.

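### The protocol's definition of death-censored graft survival counts death as a failure, so read literally it duplicates non-censored graft survival

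*Protocol*

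**What the plan says.** Protocol section 6.2 lists two graft survival outcomes under the objective that compares graft and patient survival between cohorts.

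- The first is "Graft survival (death censored) at 7 days, 3 and 12 months and 5 years following transplantation", with the bracketed definition "defined as a functioning transplant in the absence of death and re-transplantation".
- The second is the non-censored version at the same four timepoints, explained by "graft loss includes death or retransplantation".

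Section 9.8.4 repeats the pair for the long-term follow-up: "Graft survival (death censored) at 5 years post-transplant" carries the same bracketed definition, and the non-censored outcome carries the same explanation.

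The synopsis (section 3) lists the two as separate outcomes. Section 13.2 does the same for the analysis: "Patient and graft survival (censored and non-censored) will be estimated using the Kaplan-Meier method", followed by Cox regression. Nowhere does the protocol say that a recipient who dies with a functioning graft is censored at death.

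**The concern.** The label and the definition of one outcome give opposite instructions about death. The label says that death is censored. The definition says that a graft counts as surviving only if the recipient is alive and has not been re-transplanted, which makes death a failure.

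An analyst who follows the definition reports the same endpoint twice under two names. An analyst who follows the label departs from the definition the protocol gives.

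The distinction matters in this trial because it asks whether higher-risk livers can be used without worse outcomes. The primary outcome and non-censored graft survival both combine death with re-transplantation. Patient survival isolates death. Primary non-function isolates graft failure, but only in the first 10 days. Death-censored graft survival is the only listed time-to-event outcome that would show graft loss separately from day 10 to five years.

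**Working it through.** There is no stated figure to reproduce. The check is a comparison of the two definitions, followed by an illustration of what turns on it.

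**Event sets**

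- Death-censored, as defined: survival requires a functioning graft, no death and no re-transplantation. Failure is therefore death or re-transplantation, and possibly also a failed graft that is not replaced.
- Non-censored: loss includes death or re-transplantation. The word for inclusion does not rule out a failed graft that is not replaced.
- Death is a failure in both, and nothing in the wording clearly separates them.

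**Inputs for the illustration**

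- r, first-year re-transplantation: section 12.2 gives "Retransplantation in first year: around 11% for DBD, rising to 17% for DCD". These are expected rates for liver transplantation, not figures for the control cohort.
- d, first-year death without re-transplantation: not given in the protocol. Assumed to be 3%, 5% or 10%.
- Graft failure without re-transplantation is left out, because the protocol gives no rate for it.

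**Formulas**

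- Definition as written: 1 − (r + d).
- Non-censored: 1 − (r + d), the same expression.
- Death censored, with constant cause-specific hazards: re-transplantation contributes the share r/(r + d) of the total cumulative hazard, so survival is (1 − r − d)^(r/(r + d)).

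For example, with r = 0.11 and d = 0.03, the definition as written gives 1 − 0.14 = 86.0%. Censoring at death gives 0.86^(0.11/0.14) = 88.8%. The gap is 2.8 points.

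| r | assumed d | As defined | Non-censored | Death censored | Gap (points) |
|---|---|---|---|---|---|
| 11% | 3% | 86.0% | 86.0% | 88.8% | 2.8 |
| 11% | 5% | 84.0% | 84.0% | 88.7% | 4.7 |
| 11% | 10% | 79.0% | 79.0% | 88.4% | 9.4 |
| 17% | 3% | 80.0% | 80.0% | 82.7% | 2.7 |
| 17% | 5% | 78.0% | 78.0% | 82.5% | 4.5 |
| 17% | 10% | 73.0% | 73.0% | 82.0% | 9.0 |

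The definition as written and the non-censored outcome agree in every row. The death-censored value hardly moves with d, as it should. The gap follows the assumed death rate closely.

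**The case against.** The best defence is that the intent is plain. The two outcomes stand side by side under contrasting labels in sections 3, 6.2 and 9.8.4, and section 13.2 names both again. The term death censored is itself a censoring instruction. The bracketed words could be read as describing a recipient who is doing well, not as an event rule. Event and censoring coding is often left to the SAP, which is not at hand and may have it right.

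This makes the literal error less likely in practice, but it does not remove the contradiction. The protocol chose to define the outcome, used the same words in both places, and nowhere states the censoring rule. An SAP that censors deaths would conflict with that definition.

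Four stronger readings are tempting, and the protocol does not support them.

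- *Nothing in the trial separates graft failure from death.* Patient survival is listed at the same timepoints, and primary non-function is listed too. The health economics section (13.9) also keeps re-transplantation after graft failure apart from death as outcome categories. What would be lost is one time-to-event summary.
- *Both graft survival outcomes are misdefined.* Only the death-censored one is. The non-censored definition is sound.
- *The size can be taken from the control figures, as 1 − 21.8/26 = 16% lost in the first year.* The 26% in section 5.2 is utilisation from February 2016 to January 2019. The 21.8% in section 13.3 is functional utilisation in the 2018–2019 control cohort, which has further stated exclusions and 118 livers with imputed outcomes. The ratio crosses cohorts. Even if it were valid, it would be all graft loss and not deaths with a functioning graft.
- *Deaths attributed to graft failure should be counted as events.* Nothing in the protocol shows that the registry makes this attribution in both cohorts.

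**Conclusion.** The point stands as a definition that is wrong as written, for one secondary outcome, in two places. Read literally, death-censored graft survival is the same endpoint as non-censored graft survival at every timepoint from 7 days to 5 years.

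The size cannot be stated from the protocol, because it depends on the rate of death with a functioning graft. The illustration gives about 3 to 9 percentage points at 12 months. It rests on the section 12.2 re-transplantation rates, an assumed 3% to 10% first-year death without re-transplantation, and constant cause-specific hazards. No corresponding figure can be given for 5 years.

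The primary outcome, the efficacy threshold, the sample size, the significance level, patient survival and non-censored graft survival are all unaffected.

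**What to change.** In sections 6.2 and 9.8.4, replace the bracketed definition of death-censored graft survival with one that sets the event as graft failure or re-transplantation and censors recipients who die with a functioning graft at the date of death. Leave the non-censored definition unchanged. If the SAP carries the same bracketed wording, align it.

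The cost is one sentence in two places. No new data collection should be needed: graft and patient survival already come from the registry, and reporting patient survival alongside non-censored graft survival already requires deaths and re-transplantations to be identified. Section 13.2 places the long-term survival analysis after the last patient reaches five years, so the correction is useful there even if the 12-month analysis has already been programmed.
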